### 5.6 OTHER SAFETY ANALYSES

### 5.6.1 Extent of Exposure

Exposure to study drug information will be summarized descriptively as follows:

- Treatment duration (in weeks)
- Total number of administrations
- Total cumulative dose (mg)
- Number of participants with any dose administration, separately for each dose level

### 5.7 OTHER ANALYSES

### 5.7.1 Summaries of Conduct of Study

The summary of study conduct will include a description of the following items by previous treatment group and participation / non-participation in the OLE part of the parent studies:

- Number of participants enrolled
- Number of participants included in each analysis set
- Number and percentage of participants who prematurely withdrew from the study or from study treatment (including the reasons for discontinuation and the distribution of these discontinuations by time-windowed visit)
- Incidence of protocol deviations overall and by four main categories (inclusion criteria, exclusion criteria, medication and procedural)
- Number of participants with home nursing

Major protocol deviations and premature withdrawals will be listed.

### 5.7.2 Summaries of Demographics and Baseline Characteristics

Demographic and baseline characteristics (such as age, sex, race, disease stage at enrolment in the parent studies, stratification factors as reported in IxRS at randomization in the parent studies, APOEe4 status (carrier vs non-carriers and APOe4 allele's status), presence and cumulative number of ARIA-H (during the screening and double-blind part of the parent studies), history of ARIA-E in the double-blind part of the parent studies, and use and non-use of background therapy for AD at OLE baseline, participation in POSTGRADUATE PET substudies) will be summarized descriptively for the ITT and SE analysis sets.

Descriptive summaries of continuous data will present the mean, standard deviation, median, and minimum and maximum. Descriptive summaries of discrete data will include frequencies expressed in terms of number and percentage of participants.

### 5.7.3 Summaries of COVID-19 Impact on the Trials

The POSTGRADUATE study is ongoing during the COVID-19 pandemic. Consequently, to monitor the potential impact of the pandemic on the trial, we will provide a specific set of descriptive analyses related to COVID-19 by previous treatment arm and participation / non-participation in the OLE part of the parent studies for the ITT analysis set (see Section 4), including:

- Demographic and Baseline Characteristics in Participants with Confirmed/ Suspected COVID-19 (see Section 5.7.2)
- COVID-19 AEs (see Section 5.3.3)
- COVID-19 related Protocol Deviations (see Section 5.2)
- Missed doses due to COVID-19

- Study discontinuations due to COVID-19
- Remote scale administrations

### 5.7.4 Immunogenicity Analyses

Immunogenicity analyses include the evaluation for antibodies against gantenerumab (i.e., ADAs), including the determination of antibody titers if appropriate. The immunogenicity analysis set will consist of all participants with at least one ADA assessment. The results of the confirmatory assay will be presented as a frequency table summarizing results at parent study baseline and during this study or the OLE part of the parent studies.

A listing of participants with positive ADA status per confirmatory assay and titer result will be provided.

Prior to completion of the study, one or more separate cutoff date(s) for ADA samples may be established to allow expedient samples analyses and early access by third party vendors.

### 5.7.5 Biomarker Analyses

Biomarker data will be summarized for each assessment visit using descriptive statistics of absolute values as well as change from baseline values. Plasma biomarker reports will be based on the ITT analysis set. All analysis including CSF biomarkers will be based on the CSF-mITT analysis set. The following pharmacodynamic biomarkers will be analyzed:

- Cerebrospinal Fluid (CSF):
  - Total tau (tTau)
  - Phosphorylated tau (pTau 181)
  - Neurogranin
  - Neurofilament (NFL)
- Plasma:
  - Phosphorylated tau (pTau 181)
  - Amyloid-beta 42 (Abeta-42)
- MRI-derived measurements, including:
  - Volumetric changes in whole brain, ventricles, hippocampus, cortical gray or other structures

In addition, other exploratory biomarkers will be reported separately.

### 5.7.6 Amyloid PET Substudy

The main objective of the POSTGRADUATE longitudinal amyloid PET substudy is to assess changes in brain amyloid load (as measured by florbetaben or flutemetamol) over time during the treatment with gantenerumab.

The analyses described here are restricted to analyses of data assessed during this study or during the OLE part of the parent studies. Analyses across the double-blind part of the parent studies and this study will be reported separately and are not subject of this SAP. This document will focus on amyloid PET data assessed during this study or during the OLE part of the parent studies.

### 5.7.6.1 Brain Amyloid Load Analysis

Two amyloid PET ligands are allowed in this substudy according to country and site availability: florbetaben and flutemetamol. However, the same ligand has to be used for the same participant throughout the study. For all participants, the ligand that is used has to remain the same as that used previously (e.g., if a participant has been enrolled in the parent study (GRADUATE I or GRADUATE II) with a positive florbetaben PET scan, only florbetaben will be allowed and used for the longitudinal follow-up scans for this participant in this study).

Centiloid mapping will be completed for the Standard Uptake Value Ratio (SUVR) data from the two amyloid PET ligands. The aPET-mITT analysis set will be used to summarize amyloid load in centiloid by descriptive statistics for each assessment time point as well as the change from baseline by previous treatment.

#### 5.7.6.2 General Considerations on Amyloid PET Statistical Analyses

The baseline assessment will be the last amyloid PET scan before or on OLE Day 43 (time window for day 1 is +42 days) that was performed within 6 months before OLE Day 1.

With the Centiloid endpoint, data from both tracers will be pooled and analyzed together. Separate analysis by tracer with the Centiloid endpoint may also be conducted as appropriate.

Missing values will not be imputed.

Visit Windowing

The analysis of amyloid PET data will be undertaken using reporting windows as defined in

Table 2. In case of more than one assessment within a time window, the assessment with the date closest to the target (scheduled) day will be selected. The time windows are based on study days, defined as days on study since first OLE dose, with the day of first OLE dose being study Day 1 and the day before first dose being study Day -1

Because of visit windowing, data collected at an early termination visit will be summarized at the appropriate time in the trial. For participants who have discontinued treatment early, if a PET scan is performed more than 56 days (early termination visit expected 14 days after last dose, followed by time window per protocol for early termination is ±42 days) after the date of last dose, the PET scan will not be used for the analysis

Table 2 Time Windows for Amyloid PET Endpoints

Visit	Target study day	Time window
Baseline	1	-183, 43
Week 52	365	281, 449
Week 104	729	645, 813
Week 156	1093	1009, 1177
Week 208	1457	1373, 1541

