### 5.1.1 Definition of Baseline

The first dosing visit in the OLE will be considered as baseline (OLE Day 1). The last available assessment made before or on OLE Day 1 will be considered the baseline assessment if occurring within 12 weeks before or on OLE Day 1 and prior to first dose for standard-of-care examinations or within 6 months for C-SSRS, cognitive scale results and MRI scans. For ADA data, baseline will be the baseline value of the parent studies to ensure that the baseline value is before any dose of the investigational product.

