#### 5.7.7.2 General Considerations on Tau PET Statistical Analyses

The baseline assessment for tau PET is scheduled for the OLE Day 1 visit (+42 days). Note that the results of the tau PET scan do not need to be available before dosing.

The last tau PET scan available within 6 months before OLE Day 1 and up to OLE Day 43 will be considered the baseline assessment.

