#### Visit Windowing

For tau PET assessments, due to the long time between scheduled assessments, time windows, as defined in Table 4, will be used.

33

Table 4 Time Windows for Tau PET Endpoints

Visit	Target study day	Time window
Baseline	1	-183, 43
Week 52	365	281, 449
Week 104	729	645, 813
Week 156	1093	1009, 1177
Week 208	1457	1373, 1541

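### SAP 5.7.6.2 promises to place early-termination amyloid PET scans by visit window, but the windows leave gaps where eligible scans have no visit; the PET baseline and tau rules also need reconciling

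*SAP*

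**What the plan says.** **Amyloid, SAP Section 5.7.6.2 and Table 2**

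- Windows: Baseline is Days −183 to 43, then Week 52 (281–449), Week 104 (645–813), Week 156 (1009–1177) and Week 208 (1373–1541). The first OLE dose is Day 1 and the day before it is Day −1.
- Several scans in one window: "the assessment with the date closest to the target (scheduled) day will be selected".
- Early termination: "Because of visit windowing, data collected at an early termination visit will be summarized at the appropriate time in the trial". For a participant who stops treatment early, a scan is left out "if a PET scan is performed more than 56 days (early termination visit expected 14 days after last dose", plus a tolerance of 42 days).
- Baseline: the last amyloid scan "before or on OLE Day 43 (time window for day 1 is +42 days) that was performed within 6 months before OLE Day 1".

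**Tau, SAP Section 5.7.7.2 and Table 4**

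- Baseline: "The last tau PET scan available within 6 months before OLE Day 1 and up to OLE Day 43".
- Windows: "due to the long time between scheduled assessments, time windows, as defined in Table 4, will be used". Table 4 repeats the five windows of Table 2. No limit after the last dose and no rule for several scans in one window are given.

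**General rule, SAP Section 5.1.1:** "The last available assessment made before or on OLE Day 1 will be considered the baseline assessment", subject to a look-back limit. PET is not named there.

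**The concern.** A by-visit summary can show a scan only if some visit window contains it. The SAP relies on windowing to place early-termination scans and states one exclusion, the 56-day limit. If an eligible scan falls between windows, the SAP neither assigns it to a visit nor says that it is dropped. In practice it would disappear from the tables by default, against the stated intention. Since missing values are not imputed, nothing takes its place.

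The baseline rules raise a related problem. Every change from baseline depends on which scan is called baseline, and the amyloid sentence, Table 2 and the closest-to-target rule can give different answers for the same participant. For tau, the rule can choose a scan taken after dosing has started when one taken before dosing is available. At stake is which scans enter the summaries of change in amyloid and tau load, the main objective of each substudy.

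**Working it through.** **1. The SAP's own figures reproduce.** Target day = 7 × week + 1, giving 365, 729, 1093 and 1457. Each window is target ±84 days, for example 365 − 84 = 281 and 365 + 84 = 449. The baseline upper limit is 1 + 42 = 43, and the early-termination limit is 14 + 42 = 56 days. Nothing is miscalculated; the problem is what the rules leave uncovered.

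**2. Days in no window (Tables 2 and 4)**

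| Gap | Days |
|---|---|
| 44–280 | 237 |
| 450–644 | 195 |
| 814–1008 | 195 |
| 1178–1372 | 195 |
| Total | 822 |

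**3. An example.** Last dose at Week 70 is Day 7 × 70 + 1 = 491. An early-termination scan 14 days later is on Day 505, well inside the 56-day limit. Day 505 lies in the 450–644 gap, so the scan is eligible and has no visit.

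**4. How many last-dose visits lead to a gap.** Doses are given on even weeks, so a last dose at Week w is Day 7w + 1 and a scan 14 days later is Day 7w + 15. Early stopping means a last dose before Week 206: w = 0, 2, …, 204, which is 103 visits.

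| Last-dose weeks with the scan in no window | Visits |
|---|---|
| 6–36 | 16 |
| 64–88 | 13 |
| 116–140 | 13 |
| 168–192 | 13 |
| Total | 55 of 103 (53.4%) |

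For w = 0, 2 and 4 the scan falls on Day 15, 29 or 43, inside the Baseline window. Participants from the parent-study OLE start this study at about Week 36. Counting from w = 36 gives 1 + 13 + 13 + 13 = 40 of 85 (47.1%).

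For 43 of the 103 visits, every scan day from 1 to 56 days after the last dose is in a gap, so the exact timing of the scan does not rescue them.

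**5. From visits to scans.** The documents give no dropout pattern, so this step rests on assumptions. With constant dropout of 5% to 40% per year and a scan either 14 days or anywhere from 0 to 56 days after the last dose, the share of early-termination scans in no window is 53.7–61.6% counted from Day 1 and 43.7–50.1% counted from Week 36 (Day 253). If all early stops fall at Weeks 50, 52, 102, 104, 154 or 156, the share is 0%.

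**6. Baseline, rule by rule**

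| Scans on | Amyloid sentence, literal | Last scan up to Day 43 (tau rule) | Closest to Day 1 |
|---|---|---|---|
| Day 20 only | none | Day 20 | Day 20 |
| Days −10 and 40 | Day −10 | Day 40 | Day −10 |
| Days −100 and 40 | Day −100 | Day 40 | Day 40 |

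In the second row the distances to Day 1 are 10 and 39 days. The third row shows that closest-to-target can also choose a post-dose scan.

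**The case against.** **The amyloid baseline sentence is only clumsy.** Its own allowance of 42 days would have no purpose if Days 2–43 were excluded. Table 2, Table 4 and the tau sentence all point to six months as the lower bound and Day 43 as the upper. This largely stands: the literal reading is probably not intended. It does not settle last against closest to target, which differ even when Days 2–43 are allowed.

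**The tau rule is a stated choice.** The SAP says "The baseline assessment for tau PET is scheduled for the OLE Day 1 visit (+42 days") and that results need not be available before dosing. Section 5.1.1 does not name PET, and former-active participants had about two years of gantenerumab before OLE Day 1. The effect is also likely to be small for former-placebo participants: by Day 43 Protocol Table 1 has them on 2 × 120 = 240 mg, against 3 × 120 + 3 × 255 + 3 × 510 + 8 × 510 = 6,735 mg scheduled before Week 52 (3.6%). All this justifies accepting a post-dose scan when there is no earlier one. It does not explain preferring it when a pre-dose scan exists.

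**PET visits are annual, and no target falls in a gap.** True: a scheduled scan within 84 days of its target is unaffected. The gaps matter for early-termination or badly mistimed scans.

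**Early-termination PET may be rare.** PET is not in the Protocol Appendix 1 schedules, and the substudy protocols were not supplied. So the frequency is unknown. But Section 5.7.6.2 itself cites a per-protocol tolerance for early-termination scans, so it expects them to occur.

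**Conclusion.** Two items are wrong as written. The Table 2 windows cannot place the early-termination amyloid scans that Section 5.7.6.2 says will be summarized: 55 of 103 possible last-dose visits (40 of 85 from Week 36) put a scan 14 days later in no window. The amyloid baseline sentence, taken literally, disagrees with Table 2, and its choice of the last scan disagrees with closest to target. Aligning the tau rules is a cheap improvement.

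Three stronger readings are tempting and not supported:

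- A reader might take 822 of the 1,498 days from Day 44 to Day 1541 (54.9%) as the share of PET data lost. That counts calendar days, not scans, and the denominator is a choice. The true share depends on dropout and on the substudy protocols.
- A reader might infer that participants scanned on Days 2–43 will be left without an amyloid baseline. The surrounding text makes a drafting slip more likely.
- A reader might infer that tau summaries will routinely include off-treatment scans that amyloid excludes. For example, with a last dose on Day 603 and both scans on Day 703, 100 days later, amyloid drops the scan and tau counts it as Week 104. The rules do differ in this way, but Protocol Sections 4.5.13 and 4.6.1 plan only safety data and secondary endpoints after withdrawal from treatment, so such a scan is not a planned assessment in the documents supplied.

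Severity is minor. The endpoints are exploratory and descriptive, no hypothesis is tested, no primary or secondary endpoint is touched, and a participant who stops in a gap still contributes any earlier annual scan.

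**What to change.** Amend SAP Sections 5.7.6.2 and 5.7.7.2 so that amyloid and tau follow the same rules:

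1. **Baseline.** Use the last scan before the first OLE dose and within six months of OLE Day 1. Only if there is none, use a scan up to Day 43. Never use an early-termination scan as baseline. State that this rule, not closest to target, governs the Baseline window.
2. **Early termination.** Keep the ±84-day annual windows. Report early-termination scans within 56 days of the last dose that fall outside every post-baseline window in a separate early-termination row, with value, change from baseline and study day. Do not drop them or relabel them as an annual visit.
3. **Tau.** State the 56-day limit and the closest-to-target rule for post-baseline windows, as for amyloid.

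The cost is SAP wording and one extra table row per endpoint; no new data are needed. The drawback is that the row mixes participants with different exposure times, which is why the study day should be shown with it.

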### Details for Definition of Variable

The Centiloid variable will be used rather than the original SUVR, because it allows data to be combined from different tracers, by mapping SUVR values to a standardized scale. The Centiloid variable is the current common standard in the scientific community.

The primary SUVR measure of interest is computed using a weighted composite target region and whole cerebellum as reference region. The weighted composite target region is composed of (both left and right side):

- frontal lobe,
- parietal lobe,
- temporal lobe lateral,
- cingulum posterior and
- anterior cingulate gyrus

Each region is weighted by its own volume. The Centiloid conversion is a linear transformation of SUVR with tracer-specific parameters that are given below in Table 3:

### Centiloid Equation:

 $CL = SlopeCL \times SUVR + InterceptCL$ 

CL=Centiloids; SlopeCL=slope; SUVR=standard uptake value ratio of the target region; InterceptCL=intercept.

The pertinent values for the two tracers are:

Table 3 Primary Centiloid Equation Parameters

Tracer	Reference	Slope	Intercept
Florbetaben-F18	whole cerebellum	175.6	-174.2
Flutemetamol-F18	whole cerebellum	143.5	-141.1

### 5.7.6.3 Summaries of Conduct of Substudy

The summary of study conduct will include a description of the following items by previous treatment arm:

- Number of participants enrolled
- Number of participants included in each substudy analysis set
- Number and percentage of participants who prematurely withdrew from the study, substudy or from study treatment (including the reasons for discontinuation and the distribution of these discontinuations by time-windowed visit)
- Incidence of protocol deviations overall and by four main categories (inclusion criteria, exclusion criteria, medication and procedural)

Major protocol deviations, including major deviations with regard to the inclusion and exclusion criteria, will be summarized and listed. Separate tables will be provided for COVID-19-related major protocol deviations and reasons for COVID-19-related major protocol deviations.

Premature study drug discontinuation and study or substudy discontinuation, as well as reasons for discontinuations, will be summarized and listed.

The outputs will be performed on the Amyloid ITT analysis set.

### 5.7.6.4 Summaries of Demographic and Baseline Characteristics

Demographic and baseline characteristics of the participants who participate in this substudy will be summarized for the amyloid ITT analysis set as described in Section 5.7.2.

### 5.7.6.5 Safety Analyses

The safety analyses for the participants in the amyloid PET substudy will be conducted as part of the main study (POSTGRADUATE or OLE part of the parent study) safety analyses. There will not be a separate analysis of participants in this substudy.

### 5.7.6.6 Interim Analysis

To adapt to information that may emerge during the course of this study, the Sponsor may choose to conduct one or more interim analyses for administrative reasons which may include efficacy, safety, and biomarker outcomes. No interim analysis of the substudy is planned for the time of the completion of parent studies.

### 5.7.7 Tau PET Substudy

The main objective of the POSTGRADUATE longitudinal tau PET substudy is to assess changes in brain tau load (as measured with [18F]GTP1) over time during treatment with gantenerumab.

The analyses described here are restricted to analyses of data assessed during this study or during the OLE part of the parent studies. Analyses across the double-blind part of the parent studies and this study will be reported separately and are not subject of this SAP. This document will focus on tau PET data assessed during this study or during the OLE part of the parent studies.

### 5.7.7.1 Brain Tau Load Analysis

The substudy is performed with an intravenous (IV) injection of a minimum of 185 MBq (5 mCi) and up to 259 MBq (not more than 7 mCi) of [18F]GTP1 and imaging for a 30-minute scan, beginning 60 minutes following injection per PET scan.

The Tau ITT analysis set will be used to summarize tau burden in SUVR by descriptive statistics for each assessment time point as well as the change from baseline by previous treatment.

#### 5.7.7.2 General Considerations on Tau PET Statistical Analyses

The baseline assessment for tau PET is scheduled for the OLE Day 1 visit (+42 days). Note that the results of the tau PET scan do not need to be available before dosing.

The last tau PET scan available within 6 months before OLE Day 1 and up to OLE Day 43 will be considered the baseline assessment.

#### Visit Windowing

For tau PET assessments, due to the long time between scheduled assessments, time windows, as defined in Table 4, will be used.

33

Table 4 Time Windows for Tau PET Endpoints

Visit	Target study day	Time window
Baseline	1	-183, 43
Week 52	365	281, 449
Week 104	729	645, 813
Week 156	1093	1009, 1177
Week 208	1457	1373, 1541

#### Details for Definition of Variable

Statistical analyses will be conducted on tau PET Median Standardized Uptake Value Ratios (SUVR) in the following four target regions of interest. In composite target regions, each region is weighted by its own volume.

- A temporal composite target region. This region is composed of (both left and right):
  - anterior and posterior superior temporal gyrus,
  - posterior temporal lobe,
  - fusiform gyrus,
  - middle and inferior temporal gyrus.
- A medial temporal composite region not including the hippocampus, composed of (both left and right):
  - Amygdala,
  - Parahippocampus,
  - Anterior medial and lateral temporal lobe.
- Frontal lobe (both left and right)
- Parietal lobe (both left and right)

The inferior cerebellar grey matter will be used as reference region for the calculation of median SUVRs for all four target regions considered.

### 5.7.7.3 Summaries of Conduct of Substudy

The summary of study conduct will include a description of the following items by previous treatment arm:

- Number of participants enrolled
- Number of participants included in each substudy analysis set

- Number and percentage of participants who prematurely withdrew from the study, substudy or from study treatment (including the reasons for discontinuation and the distribution of these discontinuations by time-windowed visit)
- Number and percentage of participants who completed treatment, the substudy, the study
- Incidence of protocol deviations overall and by four main categories (inclusion criteria, exclusion criteria, medication and procedural)

Major protocol deviations, including major deviations with regard to the inclusion and exclusion criteria, will be summarized and listed. Separate tables will be provided for COVID-19-related major protocol deviations and reasons for COVID-19-related major protocol deviations.

Premature study drug discontinuation and study or substudy discontinuation, as well as reasons for discontinuations, will be summarized and listed.

The outputs will be performed on the Tau ITT analysis set.

